12 STATISTICAL CONSIDERATIONS

12.1 Sample Size

12.1.1 Dose Escalation

The number of participants will depend on the number of dose cohorts that will be enrolled before reaching the MTD. It is anticipated that the study will evaluate three dose levels of PF-07901801 given in combination with a fixed dose of PLD. On the basis of emerging safety and/or clinical activity data, additional dose levels may be added. The size and design of the Phase 1 dose escalation phase of the study is consistent with standard 3+3 design with the objective of determining the safety of escalating doses of PF-07901801 in combination with fixed-dose PLD and establishing PF-07901801 doses for further evaluation in the intended participant population. Based on a standard 3+3 design, up to approximately six DLT-evaluable participants may be enrolled in each dose level cohort during the Phase 1 dose escalation portion of the study; a minimum of nine and a maximum of 18 DLT-evaluable participants is anticipated.

12.1.2 Expansion Cohort

Phase 2 expansion cohort is planned to evaluate a selected PF-07901801 dose level in combination with a fixed dose of PLD. In this hypothesis-generating study, assuming an objective response rate of 10% with PLD monotherapy and an alternative of 30%, a power of 80% and one-sided Type 1 error set at 0.05, the combination will be considered worthy of further study if at least six responses are observed in the 25-participant cohort. If the dose level combination selected for further Phase 2 is determined to be not optimal or not well tolerated, an intermediate dose level, not to exceed the dose levels evaluated in Phase 1, may be implemented.

Other secondary endpoints, such as disease control, duration of response, progression-free survival and overall survival will be analyzed descriptively.

12.2 Analysis Populations

The following analysis populations are defined for the study:

Safety Population: all participants who received at least one dose of PF-07901801

DLT-Evaluable Population: all participants in Phase 1 who either experience DLT after at least one dose of PF-07901801 or did not experience a DLT and received the full dose of PLD and at least two infusions of PF-07901801 and completed safety evaluations during the 28-day Cycle 1 DLT period.

PF-07901801 and PLD Concentration Analysis Population: all participants who received at least one dose of PF-07901801 or PLD and have at least one evaluable blood sample for analysis collected.

12.3 Criteria for Evaluation

12.3.1 Safety

All participants who receive at least dose of PF-07901801 will be included in the safety analyses.

Adverse events, ECGs, laboratory data will be summarized and reviewed on an ongoing basis during the study. All adverse events, ECGs, LVEF assessments and safety laboratory abnormalities of potential clinical concern will be described. Safety data will be presented in tabular and/or graphical format and summarized descriptively by dose cohort and time where appropriate. Absolute value data and changes from baseline data will be summarized as appropriate.

Adverse events will be coded using the Medical Dictionary for Regulatory Activities (MedDRA) and severity of adverse events and laboratory abnormalities will be graded using NCI CTCAE v5 as appropriate. Incidence tables of participants with adverse events will be presented for all adverse events by maximum severity, serious adverse events, adverse events assessed as related to study drug and adverse events resulting in discontinuation of study drug.

For ECG analyses, the mean of the triplicate ECG parameters will be used as the observation for a participant at a nominal time point. Changes in ECG and laboratory measurements will be summarized.

Listings of all safety data sorted by dose cohort, participant and assessment date will be provided.

The incidence, onset time and titer of PF-07901801 directed anti-drug antibodies will be summarized descriptively. Exploratory analysis may be conducted to evaluate the possible effects of anti-drug antibodies on PF-07901801 concentrations, efficacy and safety endpoints.

CCI

12.3.4 Disease Control

Clinical efficacy will be evaluated using overall tumor response for participants with measurable disease as assessed by the investigators using RECIST v1.1 (Appendix B). Duration of response will be calculated for participants who achieve a CR or PR and is defined as the time from the date of first documented response (CR or PR) to the date of documented progression or death after achieving response. Progression-free survival will be calculated for all treated participants from the date of the first dose until the date of progression or death. Participants without progression or death will be censored at the date of last non-PD assessment. Overall survival will be calculated for all treated participants from the date of the first dose until date of death. Participants without death will be censored at the last date the participant was known to be alive. Disease control rate is defined as the percentage of participants who have achieved CR, PR, or SD lasting at least 12 weeks.

12.3.5 Biomarker and Pharmacodynamics Assessments

The details of biomarker and pharmacodynamic assessments will be described in the SAP or in a separate exploratory analysis plan. Results of biomarker and pharmacodynamic analyses will be described in the CSR to the extent possible. Due to the exploratory nature of these endpoints, the associated data analyses may not be completed at the time of the CSR preparation. If results of biomarker and pharmacodynamic analyses are not included in the CSR, they may be disseminated to the scientific community to the extent possible through presentation at scientific meetings and/or publication in peer-reviewed scientific journals.

12.4 Statistical Methods

Tabular summaries of data will be descriptive in nature (i.e., number of participants [n], mean, standard deviation, median, minimum and maximum for continuous variables and n and percent for categorical variables). For efficacy parameters, including objective response rate and disease control rate, 95% confidence intervals will be presented using the Wilson's score method. Time-to event endpoints such as DOR, PFS, and OS will be evaluated using Kaplan-Meier method.

Protocol deviations will be listed. Protocol deviations that might substantially affect efficacy analyses will be determined prior to database lock.

A more detailed description of analysis methods will be provided in the SAP to be completed prior to the clinical database lock.

13 SAFETY

Adverse events observed, mentioned on open questioning by a member of the investigator team, or spontaneously reported by the participantwill be documented. Adverse events will be documented event based. The observation phase for adverse events will start with signing the informed consent and will end at the completion of the active reporting period. Planned timepoints for all safety assessments are provided in the Study Assessments (Section 10). Unscheduled safety measurements may be obtained at any time during the study to assess any perceived safety issues.

13.1 Definition of Adverse Events

13.1.1 Adverse Event

An adverse event is any untoward medical occurrence or the worsening of a pre-existing medical condition following or during exposure to a pharmaceutical product, whether or not considered causally related to the product. Development of new disease lesions or disease progression is not considered an adverse event.

All AEs and SAEs occurring in a participant during the active collection period as described in Section 13.5.3 will be recorded on the appropriate CRF from the signature of the informed consent. All SAEs must be reported on the CT SAE Report Form to Pfizer Safety immediately upon awareness and under no circumstance should this exceed 24 hours. A worsening of a condition/disease recorded in the medical history is reportable as an AE. Documentation must be supported by an entry in the participant's source medical records. Laboratory abnormalities requiring treatment or considered by the investigator to be clinically relevant should be reported in the CRF as an AE. Each AE is to be evaluated for duration, severity and causal relationship with the IP.

For the purposes of this study, events that are unequivocally due to disease progression should not be reported as AEs unless the outcome is fatal within the active collection period. Hospitalization due to signs and symptoms of disease progression should not be reported as an SAE. If the malignancy has a fatal outcome during the study, the event leading to death must be recorded as an AE on the CRF, and as an SAE with CTCAE Grade 5 if it occurs during the active collection period. Symptoms of the disease under study/lack of efficacy should not be classified as AEs as long as they are within normal day-to-day fluctuations or expected progression of the disease.

The development of a new cancer should be regarded as an AE and will generally meet at least one of the SAE criteria. New cancers are those that are not the primary reason for study treatment and have been identified after the participant's inclusion in this study. They do not include metastases of the original cancer.

13.1.2 Serious Adverse Event

A serious adverse event is an adverse event occurring during any study at any dose of the investigational product(s) that fulfills one or more of the following:

Results in death

- Is immediately life-threatening (the participant was at risk of death at the time of the event; this does not refer to an event which hypothetically might have caused death if it were more severe)
- Requires in-patient hospitalization or prolongation of existing hospitalization
- Results in persistent or significant disability or incapacity
- Results in a congenital abnormality or birth defect
- Is an important medical event that may jeopardize the participant or may require medical intervention to prevent one of the outcomes listed above

Medical or scientific judgment should be exercised in deciding whether reporting is appropriate in other situations, such as important medical events that may not be immediately life threatening or result in death or hospitalization but may jeopardize the participant or may require medical or surgical intervention to prevent one of the other outcomes listed in the above definition. These should also be considered serious.

Examples of such events include invasive or malignant cancers, intensive treatment in an emergency room or at home for allergic bronchospasm, blood dyscrasias or convulsions that do not result in hospitalization, or development of drug dependency or drug abuse.

All serious adverse events that occur after any participant has signed informed consent, been enrolled, before treatment, during treatment, or within 30 days following the cessation of treatment, whether or not they are related to the study intervention, must be recorded on a Serious Adverse Event form.

13.2 Clarifications to Serious Adverse Event Reporting

- Death is an outcome of a serious adverse event and not a serious adverse event in itself. When death is an outcome, report the event(s) resulting in death as the serious adverse event term (e.g., "pulmonary embolism"). If the cause of death is unknown, report "Death, unknown cause" as the serious adverse event term.
- Pre-planned or elective hospitalizations including social and/or convenience situations (e.g., respite care) are excluded from serious adverse event reporting. In addition, emergency room visits and admission under 23-hour observation are excluded from serious adverse event reporting; however, such events should still be reported on the appropriate adverse event eCRF page.
- An isolated laboratory abnormality is not reportable as a serious adverse event unless the
 investigator assesses that the event meets the standard ICH criteria for a serious adverse
 event.

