13.4 Assessment of Severity

The severity rating of an adverse event refers to its intensity. The severity of each adverse event will be categorized using the NCI CTCAE v5. For any term that is not specifically listed in the CTCAE scale, intensity should be assigned a grade of 1 through 5 using the following CTCAE guidelines:

- Grade 1: Mild; asymptomatic or mild symptoms; clinical or diagnostic observations only; intervention not indicated
- Grade 2: Moderate; minimal, local or noninvasive intervention indicated; limiting ageappropriate instrumental activities of daily living

- Grade 3: Severe or medically significant but not immediately life-threatening; hospitalization or prolongation of hospitalization indicated; disabling; limiting self-care activities of daily living
- Grade 4: Life-threatening consequences; urgent intervention indicated
- Grade 5: Death related to adverse event

It is important to distinguish between serious adverse events and severe adverse events. Severity is a measure of intensity whereas seriousness is defined by the criteria under Section 13.1.2. An adverse event of severe intensity may not be considered a serious adverse event.

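### Protocol 13.2 excludes emergency-room visits and 23-hour observation from SAE reporting with no exception for events that are serious under 13.1.2, so such events could be classed as nonserious and miss the 24-hour report

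*Protocol*

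**What the plan says.** Protocol 13.1.2 makes an event serious if it meets one or more of six criteria. Immediate threat to life, in-patient hospitalization and important medical event are separate entries on that list. For situations beyond the plain criteria it adds: "Medical or scientific judgment should be exercised in deciding whether reporting is appropriate in other situations". Of important medical events that involve neither immediate threat to life, death nor hospitalization it says: "These should also be considered serious". Its examples include "intensive treatment in an emergency room or at home for allergic bronchospasm, blood dyscrasias or convulsions that do not result in hospitalization".

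Protocol 13.2 then offers clarifications. Its second bullet opens with planned, elective and convenience hospitalizations and goes on to say that "emergency room visits and admission under 23-hour observation are excluded from serious adverse event reporting". The same sentence ends by saying that "such events should still be reported on the appropriate adverse event eCRF page".

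The third bullet treats laboratory findings differently: "An isolated laboratory abnormality is not reportable as a serious adverse event unless the" investigator judges that the ICH criteria for seriousness are met.

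Protocol 13.4 says that "seriousness is defined by the criteria under Section 13.1.2". Sections 13.1.1 and 13.5.6 require every SAE to reach the sponsor's safety group within 24 hours.

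**The concern.** Section 13.2 is headed as a clarification, so site staff may well treat it as the working rule when deciding whether to file an SAE form. Read literally, it removes a class of events by where they were managed, whatever their nature, and some of those events are ones that 13.1.2 calls serious.

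The setting is relevant here. Both drugs are given by infusion. Protocol 8.8 notes that the PLD label warns of serious, life-threatening and fatal infusion reactions. The note to Table 19 lists bronchospasm as a sign of an infusion reaction and says that such reactions usually clear within 24 hours of the end of infusion, so a short stay is a plausible way to manage one. Blood dyscrasias, another of the 13.1.2 examples, resemble the leading related toxicities in the earlier study (Table 3: thrombocytopenia 21%, neutropenia 12%, anemia 9%).

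At stake are correct classification, the 24-hour report, and the counts in the serious-TEAE outputs (SAP 8.4 and planned Tables 26 to 30).

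**Working it through.** No sample size, rate or error probability enters, so there is nothing to compute. The check is to run the same event through both sections.

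| Event | Protocol 13.1.2 | Protocol 13.2 as worded | 13.2 with the exception added |
|---|---|---|---|
| Bronchospasm after an infusion, treated intensively in an emergency room, no admission | Serious (a listed example) | Outside SAE reporting; AE page only | SAE, 24-hour report |
| Convulsion treated intensively in an emergency room, no admission | Serious (a listed example) | Outside SAE reporting; AE page only | SAE, 24-hour report |
| Immediately life-threatening reaction, kept for 23-hour observation and discharged | Serious (separate criterion) | Outside SAE reporting; AE page only | SAE, 24-hour report |
| Emergency-room visit that meets no seriousness criterion | Not serious | AE page only | AE page only |
| Reaction treated entirely at the infusion site | Decided by its own features | Not touched | Not touched |

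The first three rows conflict. The last two do not, which marks the limits of the problem.

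Next, does anything else in the protocol restore the 24-hour report in the first three rows?

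- **AE page.** The entry is required, but Protocol 14.7 expects data entry generally within about two weeks. Against a 24-hour clock that is roughly 14 days instead of 1.
- **Sponsor review (13.5.4).** The sponsor reports as an SAE any nonserious event that it judges to be serious. No time limit is given, and the review needs the data to have arrived.
- **Medical monitor review (13.11).** It covers all adverse events on an ongoing basis, again with no time limit.
- **Notice of Grade 3 or higher infusion reactions.** This appears in Table 20 for PF-07901801. Table 23 for PLD has no such line, and neither table covers a convulsion or blood dyscrasia that is not an infusion reaction.
- **Adverse events of special interest (13.6).** None are defined, so there is no separate reporting route.

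Each reduces the risk; none substitutes for the investigator's 24-hour report.

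Last, which analyses are exposed? The dose-limiting toxicity definition (Protocol 5.4, SAP 8.3) rests on treatment-emergent adverse events in Cycle 1 and their attribution, and SAP 8.3 counts AEs and SAEs alike. Seriousness does not enter. SAP 8.4 also tabulates Grade 3 or higher TEAEs and infusion-related reactions whatever their seriousness. That leaves the serious-TEAE summaries and expedited reporting.

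**The case against.** The best defence is that the bullet is about hospitalization. It opens with planned and elective admissions and then continues to emergency-room visits and observation stays, so it may mean only that these encounters do not by themselves satisfy the hospitalization criterion. Section 13.4 points back to 13.1.2 as the governing definition, and 13.1.2 requires all SAEs to go on an SAE form. This may well be the intent. But the text excludes the encounters from SAE reporting, not from one criterion, and the laboratory bullet directly below shows that an exception was written where one was wanted. The defence therefore supports stating the intended meaning and does not remove the conflict.

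Three further points limit the concern, and they stand:

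- A reader might infer that serious infusion reactions will go unreported. The documents do not support that, because the same sentence of 13.2 sends these events to the AE page. The risk is misclassification and a lost 24-hour report.
- A reader might also infer that 13.1.2 makes all emergency-room treatment an SAE. It does not. It names intensive treatment for particular conditions, as examples, subject to medical judgment.
- Many infusion reactions would never reach the excluded settings. Protocol 8.3 requires administration where emergency facilities and trained staff are present, Cycle 1 PF-07901801 infusions are followed by 60 minutes of observation, and Protocol 9.1.7 does not expect reactions to be prevalent.

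**Conclusion.** The point holds as an internal contradiction in the safety-reporting text. For an immediately life-threatening event, or one of the intensively treated conditions named in 13.1.2, handled in an emergency room or a 23-hour observation stay, 13.1.2 requires an SAE report and 13.2 as worded excludes it. The event would still be captured as an adverse event but could be classed as nonserious, miss the 24-hour report and be left out of the serious-TEAE tables.

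The number of events affected cannot be estimated, since the documents give no rate for these settings. The practical effect depends on two assumptions: that some such events occur, and that a site follows 13.2 literally instead of going back to 13.1.2.

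Dose-limiting toxicity assessment does not depend on how seriousness is assigned. The itemised toxicity criteria are blacked out in the public text, so this rests on the visible definition. Correction is worthwhile because it is cheap and bears on prompt safety reporting; the trial's primary endpoints are not at issue.

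**What to change.** Reconcile 13.1.2 and 13.2. In the second bullet of 13.2, add to the part on emergency-room visits and 23-hour observation: *unless the event meets any other seriousness criterion in Section 13.1.2*. The laboratory bullet already works this way. A visit or short stay would still not make an event serious by itself, and the entry on the AE page would remain for the rest.

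The cost is one clause and possibly a few more SAE reports. No change to the SAP is needed: its serious-TEAE tables will be right once the events are classified correctly.

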13.3 Assessment of Causality

The relationship of each adverse event to administration of the study drug(s) will be assessed by the investigator after careful consideration of all relevant factors such as (but not limited to) the underlying study indication, co-existing disease, concomitant medication, relevant history, pattern of the adverse event, temporal relationship to receipt of the study medication(s) and dechallenge or re-challenge.

Study drug or study treatment refers to intravenously-administered PLD and intravenously-administered PF-07901801. The assessment of relationship to study drug or study treatment will be done for each drug separately. If the investigator feels such a distinction cannot be made, the assessment will be based on the combination of the two drugs.

The assessment of causality is based on the question of whether there was a reasonable causal relationship to the study drug in question according to the following guidelines:

RELATED: there is a reasonable possibility that the study treatment caused the event; one or more of the following criteria apply:

- The event follows a reasonable temporal sequence from administration of study treatment
- The event could not be reasonably attributed to the known characteristics of the participant's clinical state, environment or toxic factors or other modes of therapy administered to the participant
- The event follows a known pattern of response to study treatment
- The event disappears or decreases on cessation or reduction in dose of the study treatment. In some situations, an adverse event will not disappear or decrease in intensity upon discontinuation of the study treatment despite other clear indications of relatedness

UNRELATED: there is no reasonable possibility that the study treatment caused the event; one or more of the following criteria apply:

- The event does not follow a reasonable temporal sequence from administration of study treatment
- The event could be reasonably attributed to known characteristics of the participant's clinical state, concurrent illness, environment or toxic factor or other therapies administered to the participant
- The event does not follow a known pattern of response to study treatment
- The event does not disappear or decrease on cessation or reduction in dose of the study treatment, and it does not reappear or worsen when the study treatment is re-administered
- There is a clear alternative explanation

